### **12.3 Use of Information and Publication**

All information concerning study data, Ethicon's operations, patent application, formulas, manufacturing processes, basic scientific data, and formulation information supplied by the Sponsor or Sponsor designee to the Investigator and not previously published is considered confidential and remains the sole property of Ethicon. The Investigator agrees to use this information only to accomplish this study and will not use it for other purposes without the Sponsor's written consent.

The Investigator understands that the information developed in the clinical study will be used by Ethicon in connection with continued development of the EVICEL® Fibrin Sealant and thus may be disclosed as required to other clinical investigators or government regulatory agencies. To permit the information derived from the clinical studies to be used, the Investigator is obligated to provide the Sponsor with all data obtained in the study.

Any publication or other public presentation of results from this study requires prior review by Ethicon, Inc. Draft abstracts, manuscripts, and materials for presentation at scientific meetings must be sent to the Sponsor at least 30 working days prior to abstract or other relevant submission deadlines. Authorship of publications resulting from this study will be based on generally accepted criteria for major medical journals.

The Investigator understands not to use the name of Johnson & Johnson (J&J), Ethicon, ETHICON™ Biosurgery, Fibrin Sealant (EVICEL®), EVICEL® Fibrin Sealant, or any of its employees in any publicity, news release, or other public announcement, written or oral, whether to the public, press, or otherwise, related to this protocol, to any amendment hereto, or to the performance hereunder, without the prior consent of Ethicon, Inc.

## Appendix I: CDC/NHSN Criteria for Defining a Surgical Site Infection (SSI)

### Superficial Incisional SSI

Infections occur within 30 days after the operation *and* infection involves only skin or subcutaneous tissue of the incision *and* at least *one* of the following:

1. Purulent drainage, with or without laboratory confirmation, from the superficial incision.
2. Organisms isolated from an aseptically obtained culture or fluid or tissue from the superficial incision.
3. At least one of the following signs or symptoms of infection: pain or tenderness, localized swelling, redness, or heat *and* superficial incision is deliberately open by surgeon, *unless* incision is culture-negative.
4. Diagnosis of superficial incisional SSI by the surgeon or attending physician.

Do *not* report the following conditions as SSI:

1. Stitch abscess (minimal inflammation and discharge confined to the points of suture penetration).
2. Infection of an episiotomy or newborn circumcision site.
3. Infected burn wound.
4. Incisional SSI that extends into the fascial and muscle layers (see deep incisional SSI).

*Note:* Specific criteria are used for identifying infected episiotomy and circumcision site and burn wounds.

### Deep Incisional SSI

Infections occurs within 30 days after the operation if no implant is left in place or within 1 year if implant is in place and the infection appears to be related to the operation *and* infection involves deep soft tissues (e.g., fascial and muscles layers) of the incision *and* at least *one* of the following:

1. Purulent drainage from the deep incision but not from the organ/space component of the surgical site.
2. A deep incision spontaneously dehisces or is deliberately opened by a surgeon when the patient has at least one of the following signs or symptoms: fever (>38°C), localized pain, or tenderness, unless site is culture-negative.
3. An abscess or other evidence of infection involving the deep incision is found on direct examination, during reoperation, or by histopathologic or radiologic examination.
4. Diagnosis of a deep incisional SSI by a surgeon or attending physician.

*Notes:*

1. Report infection that involves both superficial and deep incisional sites as deep incisional SSI.
2. Report organ/space SSI that drains through the incision as a deep incisional SSI.

### Organ/space SSI

Infections occurs within 30 days after the operation if no implant is left in place or within 1 year if implant is in place and the infection appears to be related to the operation *and* infection involves any part of the anatomy (e.g., organs or spaces) other than the incision, which was opened or manipulated during an operation *and* at least *one* of the following:

1. Purulent drainage from a drain that is placed through a stab wound into the organ space.
2. Organisms isolated from an aseptically obtained culture of fluid or tissue in the organ/space.

3. An abscess or other evidence of infection involving the organ/space that is found on direct examination, during reoperation, or by histological or radiologic examination.
4. Diagnosis of an organ/space SSI by a surgeon or attending physician.

## **Appendix II: U.S. Center for Disease Control (CDC) Guideline for Prevention of SSI Surgical Wound Classification**

### **CLASS I/CLEAN:**

An uninfected operative wound in which no inflammation is encountered and the respiratory, alimentary, genital and urinary tracts are not entered. Clean wounds are primarily closed and, if necessary, drained with closed drainage. Operative incisional wounds that follow non-penetrating (blunt) trauma should be included in this category if they meet these criteria.

### **CLASS II/CLEAN-CONTAMINATED:**

An operative wound in which the respiratory, alimentary, genital and urinary tract is entered under controlled conditions and without unusual contamination. Specifically, operations involving the biliary tract, appendix, vagina, and oropharynx are included in this category, provided no evidence of infection or major break in technique is encountered.

### **CLASS III/CONTAMINATED:**

Open, fresh, accidental wounds, operations with major breaks in sterile technique or gross spillage from the gastrointestinal tract, and incisions in which acute, nonpurulent inflammation is encountered.

### **CLASS IV/DIRTY OR INFECTED:**

Old traumatic wounds with retained devitalized tissue and those that involve existing clinical infection or perforated viscera. This definition suggests that the organisms causing postoperative infection were present in the operative field before the operation.

Due to the fact that the primary endpoint is assessed at the 30-Day post-operative visit, it is anticipated that missing data will occur for this endpoint. Therefore, the statement “It is not anticipated that there will be any data missing for the primary endpoint, but if there is, the analysis for the ITT set will be performed considering missing data as failures” was replaced throughout the document by the following statement: “The analysis for the ITT set will be performed considering missing data as failures.”

1. STUDY OBJECTIVES

The objective of this study is to evaluate the safety and efficacy of EVICEL Fibrin Sealant (Human) for use as an adjunct to sutured dural repair in cranial surgery. The effectiveness objective of this study is to evaluate whether EVICEL Fibrin Sealant (Human) is non-inferior to DuraSeal Dural Sealant System (Control) for use as an adjunct to sutured dural repair in cranial surgery.

2. STUDY DESIGN

This is a single-blinded randomized, controlled study evaluating EVICEL as an adjunct to sutured dural closure compared to DuraSeal Dural Sealant System.

Approximately 230 subjects undergoing posterior fossa or supratentorial procedures (craniectomy or craniotomy) will be enrolled in the trial with at least 60 subjects undergoing posterior fossa procedures being randomized.

Upon completion of the sutured dural repair, the closure will be evaluated for intraoperative cerebrospinal fluid (CSF) leakage with a baseline Valsalva maneuver performed to an intra-thoracic pressure between 20-25 cm H₂O for 5-10 seconds. If a spontaneous leak is apparent immediately after dural closure, no Valsalva maneuver will be performed.

Subjects who have a CSF leak will be stratified by surgical procedure, posterior fossa or supratentorial approach, and then randomized to either EVICEL Fibrin Sealant or DuraSeal Dural Sealant System in a 1:1 allocation ratio.

Subjects will be followed post-operatively through discharge and again at 30 (-/+7) days and 60 (-/+14) days post-surgery. For the primary endpoint, the incidence of CSF leaks will be assessed up to the 30 day post-operative follow-up period. The incidence of CSF Leak will also be assessed up to the 60 day post-operative follow-up period. A CSF leak or pseudomeningocele will be reported as detected by any of the following: clinical observation, diagnostic testing, imaging or the need for surgical intervention to directly treat a CSF leak.

Randomization will be used to avoid bias in the assignment of treatment to each subject, to increase the likelihood that attributes of the subject are balanced across treatment groups, and to enhance the validity of statistical comparisons across treatment groups.

The Sponsor will provide each study site with two sets (Supratentorial or Posterior Fossa Approach) of computer-generated randomization envelopes, each bearing the sequential subject randomization number, and containing the treatment allocation and stratification. In the event that a potential subject fails intra-

operative criteria and is not randomized to the study, the unused randomization envelope should be returned to the series, and used for the next subject.

3. STUDY ENDPOINTS

The primary endpoint is the proportion of subjects that do not have a CSF leak during surgery and up to the 30-day (-/+ 7) post-operative period. A subject is declared as a success when the following conditions are met:

- absence of intra-operative CSF leak following final Valsalva maneuver, and
- absence of CSF leak or pseudomeningocele in the surgical area during the 30-day (-/+ 7) follow-up period.

A confirmed CSF leak or pseudomeningocele is diagnosed by physical examination, diagnostic testing, imaging study or the need for surgical intervention to directly treat a CSF leak during the 30-day (-/+ 7 days) follow-up at the location where randomized treatment was applied.

In addition, the following safety endpoints will be included in this study:

- Incidence of intra-operative CSF leakage following final Valsalva maneuver;
- Incidence of post-operative CSF leakage within 30 days (± 7) post-operatively;
- Incidence of post-operative CSF leakage within 60 (± 14) days post-operatively;
- Incidence of surgical site infections (SSI) according to NNIS definition and CDC classification within 30 days (± 7) post-operatively;
- Incidence of adverse events, collected from time of randomization, throughout the follow-up period until 60 days (± 14) after the procedure.

4. CHANGES IN THE CONDUCT OF THE STUDY OR PLANNED ANALYSIS

Not applicable.

5. ANALYSIS SETS

The following three analysis sets defined:

- Intent-to-treat (ITT) set consists of all enrolled and randomized subjects.
- Per-Protocol (PP) set consists of all ITT subjects who have data available for primary effectiveness endpoint and have no major protocol deviations.
- Safety set consists of all enrolled subjects who receive a study treatment.

The primary endpoint will be analyzed using the ITT and the PP set. However, the primary analysis will be based on the PP set. The ITT analysis will be considered confirmatory.

Major protocol deviations are deviations that have an impact on the primary endpoint, or that have an impact on the randomization assignment. These will be determined prior to database lock.

6. DEMOGRAPHIC AND OTHER BASELINE CHARACTERISTICS

6.1 Demographic and other baseline characteristics

Demographic and other baseline data will be summarized descriptively for subjects in each treatment group in the ITT set to assess comparability of treatment groups. The categorical data will be summarized descriptively by frequencies along with the associated percentages. The continuous data will be presented using summary statistics such as number of subjects, mean, standard deviation, minimum, median and maximum.

The following demographic variables will be summarized:

- Age;
- Weight;
- Height;
- Body mass index;
- Gender;
- Race/ethnicity;
- History of SVT, DVT/PE;
- Family history of DVT/PE;
- History of alcohol abuse;
- Smoking status.

In addition, the following screening and baseline data will be collected:

- Physical examination, including documentation of relevant medical and surgical history;
- Complete blood count (CBC) with white blood cell differential, liver function tests and electrolytes;
- Type of pregnancy test done prior to procedure (if applicable);
- Documentation of medical history including all concomitant medications during 24 hours prior to surgery;
- Review of inclusion / exclusion criteria to confirm subject eligibility.

7. PROCEDURE DATA

Procedure data will be summarized descriptively for subjects in each treatment group in the ITT set to assess comparability of treatment groups. The categorical data will be summarized descriptively by frequencies along with the associated percentages. The continuous data will be presented using summary statistics such as number of subjects, mean, standard deviation, minimum, median and maximum.

The following procedure variables will be analyzed:

- Operative procedure, including type of approach, indication for surgery and tumor type and location, if applicable;
- Operating room (OR) time;
- Procedure duration (from first incision to closure completion);

- CSF leak determination;
- Specification of treatment to which subject is randomized;
- For patients treated with EVICEL, the following data will be analyzed for first EVICEL application and second treatment of EVICEL (if applicable): method of EVICEL application, number of layers applied, indication of spontaneous leak observation, indication of Valsalva maneuver performed after randomized treatment application (if applicable), indication of CSF leak detection after Valsalva (if applicable) and definition of leak (if applicable);
- For patients treated with Control (DuraSeal), the following data will be analyzed for first DuraSeal application and second treatment of DuraSeal (if applicable): method of DuraSeal application, number of layers applied, indication of spontaneous leak observation, indication of Valsalva maneuver performed after randomized treatment application (if applicable), indication of CSF leak detection after Valsalva (if applicable) and definition of leak (if applicable);
- Total number of kits used, approximate total amount of randomized treatment used, and derived volume per kit;
- Indication of watertight closure after randomized treatment application;
- Indication of additional treatment application;
- Indication of watertight closure at the end of procedure;
- Indication and specification of additional treatments/rescue therapy applied, such as glues/sealants, sutures, hemostasis matrices, autologous and biologic/non-autologous dural patches.

In addition, the following post-procedure to hospital discharge data will be summarized:

- CSF leak and/or pseudomeningocele determination, along with the identification of the test used for diagnosis;
- Surgical site assessment, including presence of infection (brain abscess, meningitis, and/or surgical site infection), hematoma (intradural, extradural, and/or subcutaneous), and other surgical site experience;
- Wound healing assessment;
- Indication of subject presence and duration in ICU;
- Length of subject hospital stay;
- Laboratory data (complete blood count with differential, liver function tests and electrolytes).

8. EFFECTIVENESS

8.1 General methods of analysis

The Clinical Data Management and Biostatistics groups within Clinical Development at ETHICON will be responsible for the overall analysis of data from this protocol. All analyses/summaries will be produced using SAS® (Version 9.1 (EG) or later).

Effectiveness data will be summarized descriptively for subjects in each treatment group in the ITT set to assess comparability of treatment groups. The categorical data will be summarized descriptively by frequencies along with the associated percentages. The continuous data will be presented using summary statistics such as number of subjects, mean, standard deviation, minimum, median and maximum.

8.2 Primary effectiveness analysis

The primary endpoint is the proportion of subjects that do not have CSF leak during surgery and up to the 30-day (± 7) post-operative period. A subject is declared success when the following conditions are met:

- Absence of intra-operative CSF leak following Valsalva maneuver, and
- Absence of CSF leak or pseudomeningocele in surgical area during the 30-day follow-up period.

The primary effectiveness parameter will be analyzed using the ITT and Per-Protocol analysis sets. The Per-Protocol analysis will be the primary effectiveness analysis.

The analysis for the ITT set will be performed considering missing data as failures; in addition, sensitivity analyses for the ITT set will be performed considering missing data as successes, and, as worst-case, with missing data for the EVICEL[®] group considered as failures and missing data for the DuraSeal[™] group considered as successes.

The statistical hypothesis for testing the treatment difference is presented as follows:

- $H_0: \Delta \leq -0.10$ tested against the alternative hypothesis
- $H_a: \Delta > -0.10$.

where:

- Δ is the difference between the success rates of Experimental and Control (Experimental minus Control)
- -0.10 is the non-inferiority difference
- The assumed proportion of successes for Control is 0.95.

P_C is the proportion of success in DuraSeal[™] Control subjects and P_E is the proportion of success in EVICEL[®] subjects.

Two hundred and two (202) evaluable subjects (101 per arm) will achieve 90% power to detect a non-inferiority margin difference in group proportions of -0.10. The proportion of successes in the Control group is 0.95. The proportion of successes in EVICEL[®] group is assumed to be 0.85 under the null hypothesis of inferiority. The power was computed for the case when the actual proportion of successes in the EVICEL[®] group is 0.95. The one-sided significance level of the test is 0.025.

If the lower limit of the one-sided 97.5% confidence interval for Δ is greater than -0.10, then it will be concluded that EVICEL[®] is considered to be non-inferior to DuraSeal[™].

For the primary endpoint, the comparability between the surgical procedure (posterior fossa or supratentorial approach) subgroups will be evaluated using a logistic regression analysis, with success/failure for primary endpoint as dependent variable and with surgical procedure, treatment group, and interaction between surgical procedure and treatment group as independent variables included in the model. The interaction terms will be considered significant at 0.15 significance level in the logistic regression model. The effect of select demographics and baseline characteristics on the primary endpoint may also be evaluated. In addition, the primary endpoint will be compared between treatment groups using a Cochran-Mantel-Haenszel (CMH) Chi-square test adjusting for the surgical procedure at 0.05 significance level.

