#### **7.1.5 30-Day Follow-up (-/+7 days)**

The following information will be collected at the clinical follow-up approximately 30 days following surgery:

- Adverse events
- Changes in concomitant medications
- Laboratory evaluations
  - Electrolyte, blood urea nitrogen (BUN), creatinine
  - Complete blood count (CBC) with differential
  - Liver function tests
- Physical examination
  - Surgical site assessment
  - Wound healing assessment

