| 2.1.1 | Success (no CSF leak during surgery and up to 30-day visit): primary effectiveness analysis – PP set | Discrete data | G2 |
| 2.1.2 | Success (no CSF leak during surgery and up to 30-day visit): sensitivity analysis – ITT set | Missing data considered as: -Analysis#1: failures (d) Sensitivity analysis - missing data considered as: -Analysis#2: successes (d); -Analysis#3: failures for EVICEL and successes for DuraSeal (d) | G2 |
| 2.2 | Follow-up assessments | | |
| 2.2.1 | Post-surgery to hospital discharge assessment – ITT set | Presence of clinically significant changes to the subject, CSF leak and pseudomeningocele determination, along with the identification of the test used for diagnosis, surgical site assessment, including presence of infection (brain abscess, meningitis, and/or surgical site infection – superficial incisional, deep incisional and/or organ-space), hematoma (intradural, extradural, and/or subcutaneous), and other surgical site experience, wound healing assessment, indication of subject presence (all d) and duration in ICU (c), and length of subject hospital stay (c) | G2 |
| 2.2.2 | 30-day (± 7 days) and 60-day (± 14 days) follow-up assessments – ITT set | Method of contact with subject, indication of re-hospitalizations since previous study visit, presence of clinically significant changes to subject since previous study visit (for 30-day only), CSF leak and pseudomeningocele determination, along with the identification of the test used for diagnosis, surgical site assessment, including presence of infection (brain abscess, meningitis, and/or surgical site infection – superficial incisional, deep incisional and/or organ-space), hematoma (intradural, extradural, and/or subcutaneous), and other surgical site experience, wound healing assessment (all d) | G2 |
| 3 | Safety data | | |
| 3.1 | Adverse Events | | |
| 3.1.1 | Number of subjects experiencing any during/post treatment AE by category – Safety analysis set | | AS |
| 3.1.2 | Adverse events (during/post treatment) by subject, MedDRA preferred term and system organ class – Safety analysis set | | AM |

| No | Title of table/figure | Notes | Shell ¹ |
|-------|---|--|--------------------|
| 3.1.3 | Summary of during/post treatment adverse events by subject and coded terms, preferred terms occurring in $\geq 5\%$ of subjects – Safety analysis set | | AM |

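### Does the SAP leave open which late CSF leaks count as failures in the 30-day primary endpoint?

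*SAP*

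**What the plan says.** The window appears in several forms.

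- SAP 8.2, lead sentence: success belongs to subjects who "do not have CSF leak during surgery and up to the 30-day (± 7) post-operative period". The second success bullet in the same section leaves out the seven-day tolerance, as does Protocol 8.3.1.
- SAP 3, success bullet: "absence of CSF leak or pseudomeningocele in the surgical area during the 30-day (-/+ 7) follow-up period". The Protocol synopsis and Protocol 2 keep the tolerance too.
- SAP 3, confirmed event: diagnosis by examination, testing or imaging, "or the need for surgical intervention to directly treat a CSF leak during the 30-day (-/+ 7 days) follow-up", at the treated location.
- SAP 10.2.2, Table 2.1.1: "Success (no CSF leak during surgery and up to 30-day visit): primary effectiveness analysis".
- The change note at the front of the SAP, explaining why missing data are expected: "the primary endpoint is assessed at the 30-Day post-operative visit".

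Protocol 7.1.5 allows the visit seven days either side of Day 30, so Day 23 to Day 37. The Schedule of Events marks no leak assessment after that visit, although Protocol 7.1.6 asks about leaks again at the 60-day contact.

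On missing outcomes, SAP 5 limits the Per-Protocol set (the primary one) to subjects "who have data available for primary effectiveness endpoint and have no major protocol deviations". For the other set, SAP 8.2 says: "The analysis for the ITT set will be performed considering missing data as failures". Two sensitivity analyses follow, one with all missing as successes and one worst case against EVICEL.

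**The concern.** A binary primary endpoint should give each subject one outcome. Three kinds of subject seem not to have one.

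1. Visit on Day 23, leak on Day 28: a failure if the period governs, a success if observation stops at the visit.
2. Onset on Day 35, first reported at the 60-day contact: a failure by onset date, not by diagnosis date.
3. Visit on Day 23, no leak, no later contact: a success if the visit completes the outcome. If follow-up to Day 37 were required, the subject would be missing, hence outside the Per-Protocol set and an ITT failure.

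The first two affect the outcome itself, the third also affects membership of the primary analysis set. The trial is single-blinded, so a rule settled late could be chosen with results by arm in view.

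**Working it through.** **Step 1: the plan's own figure.** Inputs from SAP 8.2: success 0.95 in both arms, margin 0.10, one-sided alpha 0.025, power 90%, 101 per arm.

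n per arm = (1.960 + 1.282)² × (2 × 0.95 × 0.05) / 0.10² = 10.51 × 0.095 / 0.01 ≈ 99.8, so 100, against the stated 101.

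Power at 101 = Φ(0.10 / √(0.095/101) − 1.960) = Φ(3.261 − 1.960) = Φ(1.301) = 0.903. The stated design reproduces. It implies about 101 × 0.05 = 5 failures per arm.

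**Step 2: code the three subjects from the text.**

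| Subject | SAP 8.2 lead sentence, SAP 3 bullet | SAP 8.2 bullet (no tolerance) | SAP 3 confirmed event | Table title |
|---|---|---|---|---|
| 1. Visit Day 23, leak Day 28 | Failure | Failure | Failure | Success |
| 2. Onset Day 35, diagnosed at 60-day contact | Failure if onset counts | Not a failure | Not a failure if diagnosis date counts | Not a failure if the visit came before onset |
| 3. Visit Day 23, leak-free, no later contact | Success unless contact to Day 37 is required | Success unless contact to Day 30 is required | No event | Success |

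Subject 1 is a success only under a table title, which is a label and not a derivation rule. Protocol 9.5 collects adverse events continuously to the 60-day visit, so the Day 28 event would be on record. For subject 2, the confirmed-event sentence in SAP 3 can be read as placing the diagnosis inside the window. The leak then falls to the 60-day incidence listed as a safety endpoint. For subject 3, no section makes contact to Day 37 a condition for having the outcome. The change note points to the visit as the assessment, and the Schedule of Events makes it the last one. A visit inside the window completes the outcome on the ordinary reading.

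**Step 3: how many subjects could be affected.** The documents give no visit timing and no dates of late leaks, so the following are assumptions. Let L be the leak proportion over 30 days, spread evenly over time, and d the days from the visit to Day 37 (0, 7 or 14 for a visit on Day 37, 30 or 23), the same for every subject in the arm.

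Expected late leaks per 101 = 101 × L × d / 30.

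| L | d = 0 | d = 7 | d = 14 |
|---|---|---|---|
| 0.022 (earlier EVICEL study, Protocol 1) | 0 | 0.52 | 1.04 |
| 0.05 (whole design failure rate taken as post-operative) | 0 | 1.18 | 2.36 |

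The d = 14 column needs every subject to be seen on Day 23. The 5% row is an upper case: in the earlier study 100 − 92.1 = 7.9% of EVICEL subjects lacked watertight closure during surgery, against 2.2% with leakage afterwards, so most failures would be intra-operative. The 2.2% figure does not count pseudomeningocele, which the 5% row would cover. If leaks cluster soon after surgery, every entry is smaller.

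**Step 4: how many it would take to matter.** The SAP does not name the interval method, so two are shown. With 101 per arm and 5 DuraSeal failures, the lower limit is:

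| EVICEL failures | Wald | Newcombe |
|---|---|---|
| 5 | −0.060 | −0.067 |
| 7 | −0.085 | −0.092 |
| 8 | −0.097 | −0.105 |
| 9 | −0.109 | −0.117 |

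Wald at 8: (93 − 96)/101 − 1.960 × √((0.9208 × 0.0792 + 0.9505 × 0.0495)/101) = −0.0297 − 0.0676 = −0.097. From equal arms, three (Newcombe) or four (Wald) extra failures in EVICEL alone cross −0.10. A window rule applies to both arms. With equal late-leak rates, its expected effect on the difference is zero.

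**The case for a change.** The strongest case for acting is that no sentence ranks the wordings. Two careful programmers could differ on subject 2, and availability of the outcome is left to be understood. A late choice in a single-blinded trial is best avoided, and a line of text costs little. It is true that no last day is stated, and that the confirmed-event sentence does not clearly say whether its window governs every route of diagnosis or only surgical intervention.

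Two things limit this. First, the only real choice left, onset or diagnosis date, is a trade-off. Counting by onset captures more events. But the 60-day contact may be by telephone, so a date before Day 37 could rest on recall. Protocol 7.1.6 also names only CSF leak there, while SAP 8.4 summarises pseudomeningocele as well. Counting by diagnosis gives up a few late events but rests on documented findings. Neither is plainly better. Second, the affected subjects stay visible: adverse-event listing 7.1.1 derives days from procedure to onset, and SAP 8.4 tabulates leak findings at both follow-up visits. A reader can see whether any subject turns on the choice.

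**Conclusion.** No change follows. The missing tolerance in the SAP 8.2 bullet is a clerical slip, since the lead sentence above it and the matching bullet in SAP 3 both carry it. The visit wording in the table title is a short label. What counts as an available outcome is a gap that an analyst fills sensibly by accepting an assessment inside the window, and the rules for subjects without one are already written. Onset against diagnosis date is a fair trade-off.

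The likely size is about 0.5 to 1 subject per arm at the 2.2% leak rate, with 2.4 in the extreme case, against three or four one-sided reclassifications needed to reverse the result from equal arms. This rests on an assumed constant leak rate and assumed visit days, and on the earlier study's rate carrying over. A large excess of late leaks in one arm would weaken it; the documents give no reason to expect one.
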